## **B. Risks/Discomforts**

### **1. Risks related to the study protocol**

- As propofol will be used at sub-anesthetic dosing, the risk of cardio-pulmonary depression will be very low. Regardless, we will have appropriate monitoring in place and administration will be supervised by a board certified pediatric anesthesiologist. All appropriate rescue equipment and medications will be readily available. The investigator will be certified in PALS (Pediatric Advanced Life Support) and will follow PALS guidelines for resuscitation in the event that the patient experiences adverse cardio-pulmonary outcomes.
- To reduce the risk of medication error, the anesthesiologist and infusion nurse will both verify the correct programming of the infusion pump upon starting the study drug treatment. The Alaris IV infusion pump utilized in the SPU has capability to be programmed for mcg/kg/hr, and each pump is inspected for calibration and proper function by the CMC BioMed department. Each subject will also have a worksheet with the dosing protocol and the dose estimates based on weight (e.g. a patient who weighs 50kg would start at 1 mg/min of infusion, a patient who is 60kg would start at 1.2 mg/min, etc).

Possible side effects associated with propofol include:

- Decreased heart rate
- Irregular heart rate
- Increased heart rate
- Decreased blood pressure
- Increased blood pressure
- Pain at injection site
- Decreased breathing rate
- Rash
- Itchiness
- Uncontrolled movement
- Allergic reaction
- Propofol is a known venous irritant and administration may cause localized pain at the insertion site when the infusion is started. Pain will be self-limiting. Subjects and their parent, if applicable, will be informed of the discomfort and we will have distraction techniques in place to assist with the initial pain.
- Allergic reactions to the study medication are rare, however appropriate interventions will be available should this rare event occur.

- Risks to pregnant females or to the embryo/fetus are unknown; therefore we will screen this population for exclusion with a urine pregnancy test.
- 
- There is always risk of loss of confidentiality; the study team will protect the confidentiality of all study patients and follow all regulations and policies in place to protect patient confidentiality.

## **2. C. Alternatives**

## **3. D. Costs to the Subject**

Subjects will be responsible for all procedures done as standard care, including IV placement, costs associated with use of SPU space, inpatient admissions and related costs of hospital procedures, treatments, medication and DHE infusion therapy. The participants will not be responsible for the cost of the study drug.

## **4. E. Reimbursement of the Subjects**

Patients will not be paid for participating.

## **5. F. Confidentiality of Records**

Information about the patients will be kept confidential. The data will be stored on a password protected database accessible only to the investigators.

## **5. Sub-Study Procedures:**

None

## **8. Sources of Research Material:**

Patient medical charts will be reviewed to assess eligibility criteria and for demographic information. Additional data will be observed and recorded during study treatment, and at the 24 and 48 hour follow up telephone calls.

### **Data Collection**

- Demographic information (age, gender, ethnicity)
- Medical history
- Current medications
- Treatment Data
  - Pulse Oximetry (continuous)
  - Respiratory Rate (continuous)
  - Pulse Rate (continuous)

- NRS pain score
- Sedation scores
- Adverse events

## **11. Subject Safety and Data Monitoring:**

As stated above, appropriate monitoring will be in place with appropriate equipment and personnel. Distraction techniques will be available to assist with initial infusion discomfort.

## **12. Procedures to Maintain Confidentiality:**

All institutional procedures regarding collected personal health information will be followed. Subjects will be assigned a study number to minimize the use of identifying information. Consent forms and paper materials will be stored in a locked office in a locked filing cabinet. Electronic data will be stored on a secure, encrypted server on a password protected computer. Only members of the study team will have access to the research files.

## **13. Potential Benefits:**

1. Improved migraine abortive therapy with decreased side-effect profile available to pediatric group
2. Safety profile of propofol infusion therapy at sub-anesthetic dosing confirmed

**14. Biostatistics:** Statistical analysis will be performed by the statistician within the Department of Anesthesiology & Pain Management at UT Southwestern Medical Center.

---

Title: Low- Dose Propofol Infusion as an Abortive Treatment for Migraine Headaches in Pediatric Patients

NCT number: NCT02485418

Document date: December 29,2023

INTRODUCTION

The purpose of this statistical analysis plan (SAP) is to describe the procedures and the statistical methods that will be used to analyze and report results for study STU 042014-002 Low- Dose Propofol Infusion as an Abortive Treatment for Migraine Headaches in Pediatric Patients.

STUDY OVERVIEW

The aim of this prospective study was to evaluate the efficacy and safety of propofol administration in a hospital setting, as an abortive medication for children aged 7-18 with migraines.

We enrolled subjects who were scheduled to undergo DHE infusion for treatment of migraine headaches as part of standard medical care. Subjects were identified from the investigators' patient list, of children presenting to the Headache Clinic in the Pain Management Clinic for treatment of migraine headache or who had been admitted to the hospital for treatment of migraine headache. If the investigator determined that they were eligible, the family was contacted in advance of the visit to discuss possible participation. An investigator was present at the visit to discuss the study in further detail and answer any questions, and informed consent was obtained prior to any study procedures performed.

Prior to initiation of DHE infusion, the subjects received sub-anesthetic doses of propofol infusion:

20 mcg/kg/min for 10 minutes, followed by an increase to 30 mcg/kg/min for 10 minutes and then by an increase to 40 mcg/kg/min for 40 minutes.

If the propofol infusion was effective in resolving headache symptoms, then subjects were monitored for at least 30 minutes after termination of infusion. Outpatient subjects were discharged home.

If propofol infusion was not successful in resolving the headache, then the subjects proceeded with standard of care.

For all subjects who received a propofol infusion, follow-up occurred at 24 and 48 hours via phone call to evaluate headache status and recover information on headache symptoms and side effects.

STUDY OBJECTIVES

Primary Objective

Based on the adult and the limited pediatric data available we hypothesized that propofol infusion in sub anesthetic dose, would result in either complete resolution or improvement in headache pain scores by 50% from the baseline pain scores. Patients were assessed with a 0-10 Numeric Pain Rating Scale.

Secondary Objectives

- Duration of effect (from the end of propofol administration till discharge criteria are meet or if treatment is ineffective, till start of new therapy)
- Total propofol dose based on weight.

Study Endpoints

The propofol infusion was terminated if:

- The patient had no pain, or greater than 50% reduction in pain scores as compared to the pretreatment pain score.
- After completing 40 minutes of propofol infusion at 40 mcg/kg/min irrespective of the pain score
- If the anesthesiologist feels cardio-pulmonary depression, airway obstruction or over sedation (Ramsay Sedation Score greater than 3) had occurred.

STATISTICAL ANALYSIS

Demographic and clinical characteristics for the sample of pediatric patients who received low- dose propofol infusion as an abortive treatment for migraine headaches were described using the sample mean and standard deviation for continuous variables and the frequency and percentage for categorical variables. The mean level of headache pain score at baseline and post-treatment (10-60 minute periods and 24- and 48-hour follow-up) was compared using the dependent samples t-test. Dependent samples t-test was also used to test for differences in the mean percent change in pain severity from baseline to each post-treatment assessment period. Statistical analyses were carried out using SAS software, version 9.4 (SAS Institute, Inc., Cary, NC). The level of significance was set at $\alpha=0.05$ (two-tailed).6.2. Data Analysis General Considerations

Sample Size Considerations

Forty patients were screened, and 38 patients participated in the study.

Handling of Missing Data

Missing data will not be imputed unless otherwise specified elsewhere in this SAP.

Protocol Deviations

Important protocol deviation criteria will be established, and subjects with important protocol deviations will be identified and documented.

Important protocol deviations will be summarized and listed by category for all subjects.

Safety Analyses

All safety analyses will be performed based on the Safety Analysis Set. Descriptive statistics will be used to analyze all safety data.

Adverse Events

Adverse events will be reported during scheduled follow-up communications and documented.

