If propofol infusion is not successful in resolving headache, then the subjects will proceed with DHE infusion per standard of care. If the subject still has no relief, the study investigators will discuss further options with the subject and parents, including hospital admission for further therapy for outpatient subjects.

For all subjects who receive propofol infusion, follow-up will occur at 24 and 48 hours via phone call to evaluate headache status and recover information on headache symptoms and side effects.

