### 3. Study termination

- if patient has no pain or greater than 50% reduction in pain scores as compared to the pretreatment pain score, then outpatient subjects will be monitored in the SPU for 1 hour. If no clinically significant side effects are present after one hour, then the IV will be removed and he will be discharged with appropriate instructions from primary headache provider for home care and follow-up. Discharge criteria will follow CMC Perianesthesia Department policy for discharge, Policy Number 1.06. Inpatient subjects who have no pain will resume standard care treatment and will be discharged at the discretion of the attending service.
- if patient has less than 50% reduction in pain scores, the study investigators will continue with DHE protocol according to standard of care.

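### The 24- and 48-hour paired t-tests have no rule for pain scores taken after DHE or other later care, so the pooled change describes propofol plus later care

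*SAP*

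**What the plan says.** **The tests.** Under Statistical Analysis, the SAP states that the mean headache pain score "at baseline and post-treatment (10-60 minute periods and 24- and 48-hour follow-up) was compared using the dependent samples t-test". A second paired test covers the "mean percent change in pain severity from baseline to each post-treatment assessment period". Baseline is the pre-propofol score.

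**Who is called.** The SAP Study Overview says: "For all subjects who received a propofol infusion, follow-up occurred at 24 and 48 hours via phone call". The protocol's Concise Summary says the same.

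**What happens before the calls.** For subjects in whom propofol fails, the documents read:
- Protocol, Concise Summary: "If propofol infusion is not successful in resolving headache, then the subjects will proceed with DHE infusion per standard of care".
- Protocol, 3. Study termination: "if patient has less than 50% reduction in pain scores, the study investigators will continue with DHE protocol according to standard of care".
- SAP, Study Overview: "If propofol infusion was not successful in resolving the headache, then the subjects proceeded with standard of care".

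For inpatients in whom it works, 3. Study termination says: "Inpatient subjects who have no pain will resume standard care treatment". The documents do not say whether that care includes further abortive drugs. Under the same section, outpatients with more than a 50% reduction are discharged home.

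**Rules that come near the point.** Under Handling of Missing Data: "Missing data will not be imputed unless otherwise specified elsewhere in this SAP". The secondary outcome on duration of effect ends at discharge criteria or, if treatment is ineffective, at the start of new therapy. The pain-score tests carry no such limit.

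**The concern.** A score taken at 24 hours in a subject who has since received DHE is an observed score, not a missing one, so the missing-data rule does not reach it. Nothing else in either document says whether it is used as it stands, set aside, counted as a failure or shown separately.

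Later treatment is built into this design. Every subject was scheduled for DHE, and failures go straight to it. The protocol's Background describes inpatient DHE as six-hourly dosing for up to five days, so an inpatient failure could still be on that course at both calls. The call items listed under 4. Follow-up (pain score, time of headache return, side effects) include no question on interim medication.

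The stake is the claim about lasting benefit. Duration of effect is a goal in the protocol's Introduction and Purpose, and sustained improvement as compared with DHE is an aim under Potential patient benefit. Because the duration outcome ends at discharge criteria or new therapy, the 24- and 48-hour tests are the only planned efficacy comparison after the treatment visit. Read as evidence of lasting propofol relief, they would credit propofol with whatever the later care achieved.

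**Working it through.** The plan gives no figure to reproduce: it states neither how many subjects received later therapy nor their scores. The calculation below only shows how large the mixing could be.

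**Inputs**
- *f*, share rescued (given later therapy for propofol failure). Background cites 80% efficacy in a retrospective review of seven pediatric patients given boluses, so f = 20%. It cites 95.4% success in an adult series, so f = 4.6%.
- *b*, total percent reduction at 24 h in rescued subjects: assumed 30-60%. The protocol's 60% for DHE is a one-hour figure, so carrying it to 24 h is an assumption.
- *a*, percent reduction the same subjects would have had at 24 h on propofol alone: assumed 0 or 20%. It need not be zero, because failure under 3. Study termination means anything below a 50% reduction.

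**Formula.** With R the mean percent reduction in everyone else:
- pooled, as observed = (1 - f) × R + f × b
- propofol alone = (1 - f) × R + f × a
- shift = f × (b - a)

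**Results, in percentage points of mean percent change**

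| f | a = 0 | a = 20% |
|---|---|---|
| 20% | 0.20 × 30 to 0.20 × 60 = 6 to 12 | 0.20 × 10 to 0.20 × 40 = 2 to 8 |
| 4.6% | 0.046 × 30 to 0.046 × 60 = 1.4 to 2.8 | 0.046 × 10 to 0.046 × 40 = 0.5 to 1.8 |

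If DHE instead removes 30-60% of the pain left after a 20% propofol effect, the shift at f = 20% is 0.20 × 0.80 × 30 = 4.8 to 0.20 × 0.80 × 60 = 9.6.

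The 20% is itself soft. Since 0.80 × 7 = 5.6 is not a whole count, the failures were 1 or 2 of 7, or 14-29%.

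**Who counts as rescued.** The Concise Summary and the SAP Study Overview start later therapy when propofol does not *resolve* the headache. 3. Study termination starts it below a 50% reduction. If non-resolution is the trigger, partial responders are rescued too. The adult low end is then 100 - 82 = 18% (82% had complete resolution), not 4.6%. At 18% the formula gives 0.18 × 30 = 5.4 to 0.18 × 60 = 10.8 for a = 0, and 0.18 × 10 = 1.8 to 0.18 × 40 = 7.2 for a = 20%. Partial responders may keep more than 20%, which would make the shift smaller.

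**Direction.** The error relative to propofol alone grows with f, but the pooled change need not look better. Take R = 50, b = 30, a = 0:
- f = 20%: pooled 0.80 × 50 + 0.20 × 30 = 46, propofol alone 40, error 6.
- f = 50%: pooled 0.50 × 50 + 0.50 × 30 = 40, propofol alone 25, error 15.

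The error rises from 6 to 15 while the pooled figure falls from 46 to 40.

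**The case against.** The strongest reply is that the SAP paragraph opens by describing the sample as patients who received the infusion, so the natural reading is all treated subjects with scores as observed. That is a legitimate treatment-policy summary. The SAP does not call these tests its duration analysis and does not claim that they show lasting relief. This stands, and it is why the pooled comparison can be kept if it is labelled. It does not supply the missing label, nor any other analysis of the sustained effect that the protocol sets out to show.

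A second reply is that an uncontrolled before-after design already prevents attributing 24- and 48-hour change to propofol. This also stands. The treatment mixture is nevertheless a separate fault that can be corrected on its own.

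A reader might go further and infer that the 24- and 48-hour results are inflated by a known amount, or that propofol looks better the more often it fails. The documents support neither. The number rescued is not given, the upper figures hold only if failures would have kept no propofol relief, and the pooled change can fall as failures rise. Nor do the documents show that inpatient responders received further abortive drugs; they say only that standard care resumed.

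**Conclusion.** The concern holds in limited form. Run as written on treated subjects, the 24- and 48-hour comparisons measure propofol plus later care, and they cannot by themselves support a statement about duration or sustained improvement on propofol. This should be fixed before those results are interpreted. It does not touch the primary response or the scores during infusion, and it would be wrong to infer that it does.

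The size cannot be settled from the documents. It could be negligible if few subjects went on to other therapy, or large enough to change the reading of the 24-hour result if about a fifth or more did. The illustrative ranges rest on three assumptions: the share rescued, the persistence of the DHE effect to 24 hours, and the relief failures would have kept without it.

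**What to change.** 1. **Label and split.** Describe the all-subject 24- and 48-hour mean and percent change as including later treatment. Show the scores by recorded propofol response and, where known, by receipt of later therapy. Show inpatient responders separately.
2. **Add a sustained-response analysis, labelled post hoc.** Among all treated subjects, first treatment only (the protocol allows repeat treatments), give the proportion who met the primary response and still meet it at 24 h and at 48 h, with an exact 95% CI. Count subjects who went on to DHE or other therapy for propofol failure as failures. Report the number of missed calls.
3. **State one response definition for the analysis only.** The primary outcome speaks of improvement by 50%; the infusion-stopping and discharge text speaks of more than 50%. On whole-number scores the two differ at baselines 6, 8 and 10, where exactly half is possible.
4. **Reconcile the passages on when later therapy starts** (headache not resolved, against less than 50% reduction). No clinical rule is proposed here.

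**Cost.** SAP wording and a small analysis of up to 38 subjects. The failure count needs only the recorded response and the start of new therapy, which the duration outcome already requires. A chart check matters mainly for inpatient responders. It goes beyond the chart review described under Sources of Research Material (eligibility and demographics) and may need approval. Without it, the labelling and the split by propofol response can still be done.

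**Downside.** The 24- and 48-hour figures will probably look less favourable and the interval will be wide: a hypothetical 24/38 is 63% (95% CI 46-78%). The fix does not remove the limits of the uncontrolled before-after design or of unrecorded home medication, and the report should say so.

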#### *Primary outcome:*

Based on the adult and the limited pediatric data available we hypothesize that propofol infusion in sub anesthetic dose, will result in either complete resolution or improve the headache pain scores by 50% from the baseline pain scores. Patients will be assessed with a 0-10 Numeric Pain Rating Scale.

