### **B. Protocol**

Patients will be recruited from the investigators patients in the headache clinic or from inpatient consults to the pain service.

Patients may be identified once scheduled for DHE infusion at the CMC Special Procedures Unit (SPU) for treatment of migraine headaches, or once the pain team is consulted for inpatient subjects who have been admitted for migraine symptoms.

Upon identification of potential subjects, if the patients meet inclusion criteria, a study investigator will describe the study details as well as the alternative DHE therapy. Should the patient's guardian consent and the patient assent we will continue with the study protocol. **If consent will be obtained the study will proceed as follows:**

- A urine pregnancy test will be performed for all female of child-bearing potential as standard care in accordance with CMC policy. The patient will have an IV catheter placed as part of standard of care treatment for DHE infusion. A peripheral vein will be accessed and an infusion of Ringer lactate will be started. For the intravenous access, a topical anesthetic (i.e. j-tip or synera patch) will be used as per SPU protocol.
- Patients will be continuously monitored as per ASA guidelines to include continuous pulse-oximetry, EKG, respiratory monitoring and heart rate. The attending anesthesiologist (investigator) will be physically present at the start of study drug infusion; he will also be immediately available in the SPU or main hospital for the duration of the infusion period.

- pain scores (Numeric Pain Rating Scale) will be evaluated during study medication titration, before, every 10 minutes throughout infusion and up to one hour after termination of the infusion.
- sedation scores will be evaluated by using the Ramsay Sedation Scale before, every 10 minutes throughout infusion and up to one hour after termination of the infusion.
- The propofol will be delivered through an infusion pump (Alaris) starting at a rate of 20 mcg/kg/min for 10 minutes, followed by an increase to 30 mcg/kg/min for 10 minutes and then by an increase to 40 mcg/kg/min for 40 minutes
- The propofol infusion will be terminated if:
  - The patient has no pain, or greater than 50% reduction in pain scores as compared to the pretreatment pain score
  - After completing 40 minutes of propofol infusion at 40 mcg/kg/min irrespective of the pain score

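### The SAP tests about eight time points on two scales, each at two-sided 0.05, and does not say which result carries the efficacy conclusion

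*SAP*

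**What the plan says.** The SAP's Statistical Analysis section sets out two families of paired t-tests. The first compares the mean baseline score with the mean at "post-treatment (10-60 minute periods and 24- and 48-hour follow-up) was compared using the dependent samples t-test". The second uses the same method to "test for differences in the mean percent change in pain severity from baseline to each post-treatment assessment period". A single two-tailed level of 0.05 is given for all the analyses.

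The SAP does not print the number of assessments. Protocol section B (Protocol) schedules pain scores "before, every 10 minutes throughout infusion and up to one hour after termination of the infusion", so 10 to 60 minutes is read here as six periods. The SAP overview adds that "follow-up occurred at 24 and 48 hours via phone call to evaluate headache status", which gives two more.

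The protocol's primary outcome is that propofol "will result in either complete resolution or improve the headache pain scores by 50% from the baseline pain scores". The SAP's primary objective repeats this: "would result in either complete resolution or improvement in headache pain scores by 50% from the baseline pain scores". Neither statement gives an assessment time. Neither document gives a testing order, a multiplicity adjustment or a rule for declaring success. The protocol's Biostatistics section says only who will do the analysis.

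**The concern.** With many tests at 0.05 and no nominated one, a reader of the results cannot tell which p-value answers the trial's question. If any significant result may be cited as evidence of efficacy, the error rate of that overall conclusion exceeds 0.05, although each test taken alone is sound.

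Two features of this trial add to the problem.

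- **Timing of the SAP.** It is dated 29 December 2023, is written largely in the past tense and reports that "Forty patients were screened, and 38 patients participated in the study". A choice of time point made now cannot be shown to be independent of the data.
- **The times ask different questions.** The infusion stops at different moments for different children. Those who do not respond go on to DHE (protocol, Study termination) or standard care (SAP overview). A low score at 24 or 48 hours may therefore reflect another treatment.

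**Working it through.** **Inputs from the documents.** Level 0.05, two-sided, per test; 38 participants in a single arm; times as listed above.

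**Count.** (6 ten-minute periods + 24 h + 48 h) × 2 scales = 8 × 2 = 16 tests. The six is inferred from the scoring schedule.

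**The stated level.** One pre-specified test at 0.05 has error 1 − 0.95 = 0.05, so the SAP's figure is reproduced for a single test. It is not reproduced as the error rate of a conclusion that any one of several tests could support.

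**Independence benchmarks.** 1 − 0.95^8 = 0.337 and 1 − 0.95^16 = 0.560. The second is not a realistic error rate. The two scales use the same scores at the same times, and in simulation they gave the same decision in about 99% of cases.

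**Simulation with correlation.** Paired t-tests, n = 38, eight times, no true change, 20,000 replicates. These assumptions are not in the documents: normal changes with SD 2, whole-number baselines from 6 to 10, complete data, and the between-time correlation of the changes as shown.

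| Correlation of changes | One named test | Any of 8 raw-score tests | Any of 16 tests |
|---|---|---|---|
| Equal, 0 | 5.0% | 34.1% | 37.4% |
| Equal, 0.3 | 5.0% | 29.9% | 32.8% |
| Equal, 0.5 | 5.2% | 25.8% | 28.2% |
| Equal, 0.7 | 5.0% | 19.4% | 21.4% |
| Equal, 0.9 | 4.9% | 12.3% | 13.6% |
| AR(1), 0.7 | 4.8% | 25.1% | 27.7% |
| AR(1), 0.9 | 4.8% | 16.4% | 18.0% |

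Repeat runs moved the ends of these ranges by about one percentage point, so the ranges are about 12% to 33-34% for eight tests and 14% to 37-38% for 16.

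**Where in the range.** All changes share one baseline. If baseline and later scores have equal variance and a common correlation, with residual variance s² around each child's own level, two changes have covariance s² and variance 2s² each. Their correlation is then s²/2s² = 0.5. On that row the error is about 26% for eight tests and 28% for 16. Zero correlation is an upper extreme.

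**If all the tests were kept with adjustment.** Bonferroni over 16 tests uses 0.05/16 = 0.003125 each, and the simulated overall error is 1.0% to 2.9%. Over the eight times on one scale it uses 0.05/8 = 0.00625, with 1.7% to 5.1% (the top value is 5% within simulation error). Holm also holds 0.05 and is less strict.

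**Can a time be read out of the documents?** No. The longest infusion is 10 + 10 + 40 = 60 minutes, so 10-60 minutes could run from infusion start. The SAP calls these periods post-treatment, and scoring also continues for up to an hour after the infusion ends, so they could equally run from its end.

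**The case against.** The strongest reply is that the SAP claims no family-wise error rate. It sets a level for each test, does not call the t-tests confirmatory and never says that one significant result is enough. Requiring every test to be significant would cause no inflation. This stands in part: no single test is wrong, and the gap is an undefined decision rule. But nothing in either document excludes the reading under which the error is inflated.

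A second reply is that the primary hypothesis is a 50% improvement, so a significant mean change at 10 minutes would not meet it. That is correct, and a reader should not infer that any of the 16 p-values could by itself satisfy the stated primary outcome. However, the SAP describes no analysis of that outcome, so the t-tests are the only inferential efficacy results it offers.

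A third is that multiplicity is a lesser threat than the absence of a control group. Entry requires a score of 6 or more, so scores may fall through regression to the mean even at one pre-named time. This also stands. The 5% in the table for a single test assumes no true change in mean score, whatever the cause.

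Two stronger readings are not supported. The 56% figure should not be quoted as the actual error, because it needs 16 independent tests. And the SAP's date shows only that it was written after enrolment. It does not show that a favourable time point was selected.

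**Conclusion.** The point holds as an undefined decision rule with a measurable consequence. Each test keeps its own two-sided 0.05. If any significant result may support efficacy, the overall chance of a false positive with no true change is about 12% to 33-34% for the eight raw-score tests and 14% to 37-38% for all 16, or roughly three to seven times 0.05.

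This rests on an inferred count of six ten-minute periods, 38 children with complete data, and assumed correlations of 0 to 0.9. The documents give no correlation, so the whole range should be shown. The SAP does not impute missing scores, so the number analysed may differ between times. If the true effect is large, the p-values may survive adjustment; that would limit the practical damage but would not supply the missing rule.

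**What to change.** 1. State in the SAP that the efficacy conclusion rests on one analysis: the protocol's responder outcome (complete resolution or 50% improvement) at one defined time, with the time origin given. Report it as a proportion with an exact 95% confidence interval. Two workable choices are 60 minutes from infusion start, or the last score at or before the end of infusion and before any DHE or other new therapy.
2. Disclose that this choice was made after enrolment.
3. Report the other times and all percent-change tests as secondary, either with Holm-adjusted p-values or as estimates with intervals only. Note that 24 h and 48 h scores may reflect DHE or standard care.
4. Reconcile the monitoring statements. The protocol's Concise Summary and the SAP overview give at least 30 minutes after the infusion; the protocol's Study termination section gives 1 hour for outpatients. This decides which scores exist. A child whose infusion stops at 10 minutes might be observed only to 10 + 30 = 40 minutes under the 30-minute statement, but to 10 + 60 = 70 under the 1-hour statement.

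The cost is SAP wording and one adjusted column, with no new data. Some p-values will become less favourable. The choice remains post hoc, and none of this deals with regression to the mean in a single-arm design.
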